6.5.4.2 Multivariate display of immunogenicity endpoints

Data-visualization techniques may be used to explore the relationship among immunogenicity readouts. The set of readouts may be based on one of the primary endpoints (eg, nAb, BAMA, ICS), on the set of primary endpoints, or on immunogenicity endpoints that also include secondary or exploratory endpoints. To understand the relationship between pairs of readouts, scatter plots may be used when the number of readouts is small; for a larger number of readouts, a heatmap showing the degree of correlation between any two pairs may be used. Principal component analysis (PCA) and associated ‘biplots’ of the scores and loadings are particularly useful to understand associations between readouts, especially when readouts are correlated (61). PCA is a method to reduce the dimensionality of the number of readouts to a smaller set of values (principal components) that are normalized linear combinations of the readouts in such a way that the first principal component accounts for the most variability in the data and subsequent components, while maximizing variability, are uncorrelated with each other. A ‘biplot’ displays the first and second principal component scores and principal component loadings. The x-axis is the value from the first principal component and the y-axis is the second principal component, where each axis label includes the percentage of variation in the total set of readouts captured by the principal component. The top axis is the first principal component loadings and the right axis is the second principal component loadings. An arrow is drawn for each immunogenicity readout (eg, Env-specific CD4+ T cell polyfunctionality score [PFS], Env-specific CD8+ T cell total magnitude) from the origin to the point defined by its first 2 principal component loadings. The length of the arrow represents the amount of total variation of the set of readouts captured by the given readout. The direction of an arrow conveys the extent to which the variation of a readout is in the direction of the first or second principal component. The angle between 2 arrows conveys information about the correlation of the 2

readouts, with a zero-degree angle denoting perfect correlation and a 90-degree angle denoting no correlation. Each arrow on the biplot is labeled by the immunogenicity readout it represents. A biplot is annotated with key meta-information, such as the treatment arm (most common application) or a demographic category. Depending on the application, K-means clustering and hierarchical clustering may also be applied for multivariate graphical display of immunogenicity readouts.

6.5.4.3 Primary analyses of neutralization magnitude-breadth curves

The area-under-the-magnitude-breadth curve (AUC-MB) to non matched (heterologous) tier 2 HIV-1 Env-pseudotyped viruses in the TZM-bl assay (62) will be computed for each participant with evaluable neutralization data, as described in Huang et al, 2009 (63). AUC-MB to a vaccine-matched panel may also be computed when the panel consists of at least 3 isolates. Dunnett's procedure will be applied with 2-sided alpha = 0.05 to determine which of the 3 vaccine groups (Groups 6-8 in Part B) have a significantly higher mean AUC-MB than that of the pooled baseline samples from Groups 6-8, as described in Liu et al, 1997 (64) (see their formula [1.1]). This procedure will be applied to construct 95% CIs about the 3 differences in mean AUC-MB for each vaccine regimen (Groups 6-8) versus the pooled baseline samples from Groups 6-8, which simultaneously have at least 95% coverage probability.

Select the best vaccine regimen among those passing the tier-2 screen

The vaccine regimens that passed the tier-2 screen will be ranked by the estimated mean of the AUC-MB curves. The vaccine regimen with the highest estimated mean will be selected as the best regimen.

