* In Part A, up to 20 participants may be enrolled if needed for safety evaluations. Additional participants may be enrolled to ensure the availability of 2-week safety data from at least 3 participants per group. Refer to the HVTN 303 Study Specific Procedures (SSP) for further details.

§ In Part B, up to 50 participants may be enrolled if needed for safety evaluations. Additional participants may be enrolled to ensure the availability of 2-week safety data from at least 15 participants per group. Refer to the HVTN 303 SSP for further details.

† Total up to 70 participants can be enrolled if needed for safety evaluations. Refer to the HVTN 303 SSP for further details.

Notes:

***Vaccination in Part B starting from Week 8 onwards did not take place.

Actual Ns for Group 6, 7 and 8 were 10, 10 and 9 respectively. In Part B total 29 participants were enrolled.

Part A of the study may begin with direct enrollment of participants into the following groups simultaneously:

- Group 1 with no more than 1 participant enrolled per day for the 3 participants.
- Group 3 with no more than 1 participant enrolled per day for the 3 participants.

After Groups 1 and 3 have been fully enrolled, the study will be placed on a safety hold. No additional enrollments will proceed until the Protocol Safety Review Team (PSRT) has determined it is safe to do so. Once all of the reactogenicity and 2-week safety data from at least 6 participants have been submitted to the database, the PSRT must assess the accumulated product-specific data as showing no significant safety concerns before proceeding with enrollment of Groups 2, 4 and 5. If the PSRT has determined it is safe to proceed after reviewing data from Groups 1 and 3, the following groups may begin simultaneously:

- Group 2 with no more than 1 participant enrolled per day for the 3 participants
- Group 4 with no more than 1 participant enrolled per day for the 3 participants
- Group 5 with no more than 1 participant enrolled per day for the 3 participants

Once Groups 2, 4 and 5 have been fully enrolled, the study will be placed on a safety hold before proceeding with Part B. Once all of the reactogenicity and 2-week safety data from at least 9 participants have been submitted to the database, the PSRT must assess the accumulated product-specific data as showing no significant safety concerns before proceeding with enrollment of Part B.

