For the 500-mcg groups, 5 of 5 (100.0%) IM recipients and 3 of 5 (60.0%) SC recipients reported at least 1 mild systemic symptom. Mild myalgia was the most frequent symptom, reported by 4 of 5 (80.0%) IM recipients and 1 of 5 (20.0%) SC recipients. Mild malaise was reported by 2 of 5 (40.0%) IM and SC recipients, respectively. Mild headache was reported by 1 of 5 (20.0%) IM recipients and 1 of 5 (20.0%) SC recipients. Mild nausea was reported by 1 of 5 (20.0%) SC recipients. All events resolved within the solicited period. There were no reports of fever or severe systemic solicited reactogenicity symptoms.

Immunogenicity:

Immunogenicity of Trimer 4571 was evaluated by measurement of the trimer-specific antibody in serum samples by Electrochemiluminescence (ECLIA) using a Meso Scale Discovery (MSD) platform at baseline and at 2 weeks after the third product administration. Trimer 4571-specific antibody titers were below the negative cut off values in all groups at baseline. All dose groups displayed detectable antibody responses at 2 weeks after regimen completion (week 22) with the geometric mean AUCs of 674 (95% CI 50-9011), 924 (95% CI 175-4880), 2,529 (95% CI 387-16515), and 1,368 (95% CI 551-3397) for the 100-mcg IM, 100-mcg SC, 500-mcg IM, and 500-mcg SC dose groups, respectively.

Trimer 4571 induced antibodies that were detected by antigen (Ag)/antibody (Ab) Combination HIV testing in participants who confirmed to be HIV negative by polymerase chain reaction (PCR). This reaction is referred to as vaccine-induced seropositivity (VISP). The VRC 018 trial used the VITROS 3600 system Ag/Ab detection assay at the NIH Clinical Center for clinical testing. Samples collected from 7 of 16 participants (43.8%) were reactive in the assay, and therefore seropositive, but participants were confirmed as HIV negative by PCR. Of the 7 participants who were seropositive, 1 was a 100-mcg recipient and 6 were 500-mcg recipients. Six of 7 participants with VISP reverted back to non-reactive on later testing. It is unknown whether the remaining 1 participant (500-mcg recipient) reverted back to non-reactive, as the final follow-up visits were conducted by the telephone, but blood samples were not collected due to the coronavirus disease 2019 (COVID-19) public health emergency stay-at-home orders.

II. NIH-19-I-0069 Phase 1 Study (NCT03878121) [Source: Information provided by Vaccine Research Center (VRC)]

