6.2.1 Sample size calculations for immunogenicity

The main goals of this trial regarding immunogenicity outcomes involve assessing the ability of FP-conjugate and Trimer 4571 vaccines alone or co-administration to elicit antibody binding FP and envelop trimer antigens and mapping FP-specific serum neutralizing activity induced by the prime vaccines regimens in Groups 5-8 and prime boost vaccines regimens in Groups 7-8. No adjustment for multiple comparisons will be made for the use of multiple assays. The precision with which the true response rate can be estimated from the observed data depends on the true underlying response rate and the sample size. Two-sided 95% CIs for the response rate based on observing a particular rate of responses in the vaccinees is shown in [Table 6-3](#). Calculations are done using the score test method (52). The sample size of n = 13 (Groups 5-6) and n=9 for each of Groups 7 and 8 will be used to evaluate the immunogenicity post the 1st vaccination induced by the vaccination; the sample sizes of n=4, 5 for Groups 7-8 will be used to evaluate the immunogenicity post the 2nd vaccination.

Table 6-3 Two-sided 95% confidence intervals for the true response rate based on observing a particular rate of responses in the vaccinees (n =4, 5, 9, 13)

No. of responses	Observed response rate (%)	95% Confidence interval
2/4	50	[15, 85]
4/4	100	[51, 100]
2/5	40	[11.8, 76.9]
4/5	80	[37.6, 96.4]
3/9	33.3	[12.1, 64.6]
6/9	66.7	[35.4, 87.9]
9/9	100	[70.1, 100]
3/13	23.1	[8.2, 50.3]
6/13	46.2	[23.2, 70.9]
9/13	69.2	[42.4, 87.3]

As shown in [Table 6-4](#), there is limited power for a formal comparison of immunogenicity response rates between Group 7 (n=9) and Group 8 (n=9). For either 80% or 90% power, the sizes of differences that the trial is powered to detect are fairly large. These calculations use a Fisher exact 2-sided test with a type I error rate of 0.05.

Table 6-4 Power for comparison of response rates between 2 arms (n1 = 9, n2 = 9)

True response rate Arm 1 (%)	Minimum true response rate in Arm 2 in order to detect a difference	
	80% power	90% power
10	83	91
20	92	99
30	99	

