6.5.4.4 Secondary analyses of neutralization magnitude-breadth curves

Superiority comparisons of vaccine regimens passing the tier-2 screen

For the set of vaccine regimens that passed the tier-2 screen, an F-test will be performed for whether any of the mean AUC-MBs differ. If this test is not significant ($p\text{-value} > 0.05$), then the conclusion will be that there were no significant differences in mean AUC-MBs among the vaccine regimens that advanced. If the F-test is significant, then simultaneous 95% CIs about the mean-differences in AUC-MBs will be reported. These CIs are computed as the estimated mean-difference plus or minus $t_{N-m,025}$ multiplied by the square-root of $S^2 (1/n_i + 1/n_j)$, where $t_{N-m,025}$ is the 97.5th percentile of a t-distribution with $N - m$ degrees of freedom, where N is the total number of vaccine recipients evaluated (summing over the advanced vaccine regimens) and m is the number of advanced vaccine regimens. In addition, S^2 is an estimate of the common sample variance of the AUC-MB, whereas n_i and n_j are the sample sizes of evaluable participants

for vaccine regimens i and j being compared. Following Fisher's least significant difference procedure, the pairs of vaccine regimens with this CI, excluding zero, are deemed to have a significant difference. Nominal (unadjusted) 95% CIs about pairs of vaccine arms will also be reported.

Omnibus comparison of magnitude-breadth distributions

The analyses of magnitude-breadth described above are based on the endpoint area-under-the-curve, which is interpreted as the average \log_{10} half-maximal inhibitory concentration (IC50) to the set of isolates in the test panel. Use of this endpoint is maximally statistically powerful if 1 vaccine arm has greater magnitude and breadth than the comparator vaccine arm, but may miss an effect wherein 1 vaccine arm has greater magnitude and the comparator vaccine arm has greater breadth. Therefore, a secondary analysis may compare the distribution of magnitude-breadth curves among vaccine arms using the test statistic $\max|B_d^G|$ from Huang, et al (63), which is designed to detect general differences in magnitude-breadth curve distributions.

Selecting the best vaccine regimen among those passing the tier-2 screen

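### Tier-2 neutralization screen: Dunnett's procedure against the same participants' pooled baselines does not assure the stated 95% simultaneous coverage

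*Protocol*

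**What the plan says.** Protocol Section 6.5.4.3, still headed as a primary analysis, computes an area under the magnitude-breadth curve (AUC-MB) per participant. It then states: "Dunnett's procedure will be applied with 2-sided alpha = 0.05 to determine which of the 3 vaccine groups" in Part B have a "significantly higher mean AUC-MB than that of the pooled baseline samples from Groups 6-8". Intervals for the three mean differences are to be built by the same procedure, "which simultaneously have at least 95% coverage probability". For the method it points to a formula in a cited paper.

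Groups that pass are ranked by mean AUC-MB and the highest is named best regimen. In Section 6.5.4.4 they go on to pairwise comparisons, where "S^2 is an estimate of the common sample variance of the AUC-MB". One selection step there uses a pooled placebo arm as comparator, although Section 9.2.1 says the trial has no placebo.

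Neither section provides for within-person pairing or for unequal variances in this comparison. The SAP covers safety only (SAP Section 2).

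**The concern.** Dunnett's procedure is built for several treatment groups and a separate control group, all independent and sharing one variance. Here the control is the Day 0 sample of the same people whose later samples form the treatment groups.

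This has two consequences, which act in different directions. Ignoring a positive within-person correlation makes the intervals too wide. Pooling a low-variance baseline block with more variable post-vaccination values makes the common SD too small, and the intervals too narrow.

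The second pattern is plausible. Participants are HIV-negative and have had no investigational HIV vaccine, so baseline neutralization may sit near the assay floor. In the earlier Trimer 4571 study (Protocol Section 2.10.1.1), "Trimer 4571-specific antibody titers were below the negative cut off values in all groups at baseline", while the post-vaccination geometric mean in one three-person group was 674 with an interval of 50 to 9011. Those are binding data, so the support is indirect.

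At stake is the gate that decides which regimens are ranked, compared and named best.

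**Working it through.** **Inputs.** Three comparisons at 2-sided alpha 0.05 (Section 6.5.4.3). Group sizes: "Actual Ns for Group 6, 7 and 8 were 10, 10 and 9 respectively" (Section 1.5), so the pooled baseline has N = 29. Section 6.2.1 gives "The sample size of n = 13 (Groups 5-6) and n=9 for each of Groups 7 and 8" after the first vaccination; that implies 10/9/9, since Group 5 has 3, and changes the results by no more than 0.5 points. Assumed, because the documents give neither: the baseline-to-post SD ratio and the within-person correlation ρ. Data are simulated as normal, with 40,000 or more runs per scenario.

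**Interval.** d_i ± c·S·√(1/n_i + 1/N), where d_i is group i's post-vaccination mean minus the pooled baseline mean. S² has 58 − 4 = 54 df, and c = 2.451.

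**Reproducing the plan's figure.** With independent comparator values and equal SDs, simulated coverage is 94.9%. It is 95.0% for 10/9/9 against 28 and for the originally planned 15/15/15 against 45. So the 95% is correct under those conditions.

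**What changes with the actual comparator.**
- True variance: Var(d_i) = σ_i²/n_i + σ_b²/N − 2ρσ_iσ_b/N.
- What the interval uses: E[S²]·(1/n_i + 1/N), with E[S²] = (28σ_b² + 9σ_6² + 9σ_7² + 8σ_8²)/54.

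*Equal SDs of 1, ρ = 0.5, n_i = 10.* Used: 0.1000 + 0.0345 = 0.1345. True: 0.1345 − 0.0345 = 0.1000. SE ratio √1.345 = 1.16. The effective critical value is 2.451 × 1.16 = 2.84, which is conservative.

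*Baseline SD 0.25, post SD 1, ρ = 0, n_i = 10.* E[S²] = (28 × 0.0625 + 26)/54 = 0.514. Used: 0.514 × 0.1345 = 0.0691. True: 0.1000 + 0.0022 = 0.1022. SE ratio √(0.0691/0.1022) = 0.822. The effective critical value is 2.02, which is too small for three comparisons.

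*Group 8 at SD 1, everything else at 0.25, ρ = 0.* E[S²] = (46 × 0.0625 + 8)/54 = 0.201. Used: 0.201 × (1/9 + 1/29) = 0.0293. True: 0.1111 + 0.0022 = 0.1133. SE ratio 0.509. The effective critical value is 1.25.

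**Simulated results, from ρ = 0 to ρ = 0.8.** A false pass means at least one group is declared higher when all means are equal (nominal about 2.5%).

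| Baseline SD / post SD | Joint coverage | False pass |
|---|---|---|
| 1 | 95.0% to 99.4% | 2.5% to 0.3% |
| 0.75 | 92.4% to 98.0% | about 4% to 1% |
| 0.5 | 88.8% to 94.6% | 5.7% to 2.8% |
| 0.25 | 85.1% to 88.4% | 7.7% to 6.1% |
| near 0 | 83% to 84% | about 9% to 8.5% |
| baseline and two arms 0.25, one arm 1 | 76.8% to 82.1% | 11.5% to 8.8% |

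With equal SDs, coverage is 99.7% at ρ = 0.95. It drops below 95% only if ρ is negative (92.9% at −0.3).

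**Own-baseline alternative.** Paired t intervals for the change within each group, each at 0.05/3, jointly cover 94.9% to 95.4% in every normal scenario. With baseline at the floor and skewed post-vaccination values (an assumed share of responders with exponential or lognormal magnitudes), the same intervals cover only about 38% to 83%. The false-pass rate of the paired test stayed at or below about 2.5% in every no-effect scenario run.

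**The case against.** Several points on the other side are sound.

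- *A reader might infer that the 95% statement simply fails.* It does not: with equal SDs and ρ from 0 to 0.95, coverage is 95.0% to 99.7%, which satisfies it.
- *A reader might blame the reuse of participants.* Non-negative correlation raises coverage; the shortfall comes from unequal variance.
- *A reader might take the two-sided miss rate of 12-16% as the false-pass rate.* A group passes only if its mean is higher, so the upper tail is what counts.
- The equal-means, unequal-spread null is awkward at an assay floor. Values cannot fall below the floor, so more spread tends to mean a higher mean, and a pass is then correct. If nobody responds, post-vaccination values are floored too and the spreads match. Under one assumed left-censored null, false passes were 4.6% to 6.4%: smaller than the worst rows above, but still over 2.5%.
- The own-baseline method is not exact for floored, skewed data. With 20-50% responders it covered 39-80%, against 76-81% for the planned intervals.
- Section 6.5.4.1 allows transformation to stabilize variance and, where much data is missing, models for censored outcomes. The cited formula could not be inspected. Transformation does not cure values tied at a floor, and the censored models are not offered for this screen.
- Version 2.0 makes MSD binding the primary immunogenicity endpoint (Section 3.1), lists neutralization mapping as exploratory (Section 3.2) and makes neutralization assays optional (Section 2.6).

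What survives is that an unconditional coverage statement is attached to a procedure whose conditions the comparator does not meet.

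**Conclusion.** The point holds in limited form. The stated simultaneous coverage is not assured; it depends on an SD ratio and a correlation that the documents do not give. It is met, with wasted precision, when spreads are equal and correlation is not negative. It falls to about 83-95% when the baseline SD is half the post-vaccination SD or less, and to about 77-82% when one arm alone becomes variable. In that last case the loss falls on the interval of the arm that responds variably, which is the kind of arm the screen is meant to judge. The matching false-pass rates are about 3-9% and 9-11.5%, against 2.5%.

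These figures assume normal data and ρ between 0 and 0.8. The premise of a floored baseline rests on binding titers from another study, not on AUC-MB data. The documents do not support saying that coverage fails in every case. The practical weight is modest because neutralization is now exploratory, but the section keeps its primary heading and still selects a best regimen, so it should be corrected if the analysis is run.

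**What to change.** - In Section 6.5.4.3, base the screen on each participant's change in AUC-MB from own baseline. Test it within each of Groups 6, 7 and 8 by a paired t test or a sign-flip permutation test, chosen in advance, with Holm across the three groups. Drop the pooled baseline as a control arm.
- Report Bonferroni intervals for the mean change, and delete the unconditional coverage statement. Say that the intervals are approximate and may under-cover when values are floored and skewed.
- Avoid the signed-rank test as the main choice. Holm's first threshold is 0.05/3 = 0.0167. Six non-zero changes, all positive, give at best 2/2^6 = 0.031; seven are needed (2/2^7 = 0.0156) out of 9 or 10 participants. A sign-flip test has the same limit if changes are exactly zero, so the plan should also say how floored values are handled.
- In Section 6.5.4.4, replace the placebo comparator with the same own-baseline comparison.
- Align the heading of Section 6.5.4.3 with the exploratory status of neutralization.

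The cost is wording only, since Day 0 serum was scheduled for every Part B group. Intervals become wider when baseline is at or near the floor: at SD ratio 0.25, ρ = 0.5 and n = 10, the mean full width is 1.63 post-vaccination SDs against 1.28 for the planned interval, whose joint coverage there is 87.3%. With equal SDs and ρ = 0.8 they become narrower, 1.14 against 1.78.

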6.5.4.4 Secondary analyses of neutralization magnitude-breadth curves

Superiority comparisons of vaccine regimens passing the tier-2 screen

For the set of vaccine regimens that passed the tier-2 screen, an F-test will be performed for whether any of the mean AUC-MBs differ. If this test is not significant ($p\text{-value} > 0.05$), then the conclusion will be that there were no significant differences in mean AUC-MBs among the vaccine regimens that advanced. If the F-test is significant, then simultaneous 95% CIs about the mean-differences in AUC-MBs will be reported. These CIs are computed as the estimated mean-difference plus or minus $t_{N-m,025}$ multiplied by the square-root of $S^2 (1/n_i + 1/n_j)$, where $t_{N-m,025}$ is the 97.5th percentile of a t-distribution with $N - m$ degrees of freedom, where N is the total number of vaccine recipients evaluated (summing over the advanced vaccine regimens) and m is the number of advanced vaccine regimens. In addition, S^2 is an estimate of the common sample variance of the AUC-MB, whereas n_i and n_j are the sample sizes of evaluable participants

for vaccine regimens i and j being compared. Following Fisher's least significant difference procedure, the pairs of vaccine regimens with this CI, excluding zero, are deemed to have a significant difference. Nominal (unadjusted) 95% CIs about pairs of vaccine arms will also be reported.

Omnibus comparison of magnitude-breadth distributions

The analyses of magnitude-breadth described above are based on the endpoint area-under-the-curve, which is interpreted as the average \log_{10} half-maximal inhibitory concentration (IC50) to the set of isolates in the test panel. Use of this endpoint is maximally statistically powerful if 1 vaccine arm has greater magnitude and breadth than the comparator vaccine arm, but may miss an effect wherein 1 vaccine arm has greater magnitude and the comparator vaccine arm has greater breadth. Therefore, a secondary analysis may compare the distribution of magnitude-breadth curves among vaccine arms using the test statistic $\max|B_d^G|$ from Huang, et al (63), which is designed to detect general differences in magnitude-breadth curve distributions.

Selecting the best vaccine regimen among those passing the tier-2 screen

For each vaccine regimen that passes the tier-2 screen, the best vaccine regimen will be deemed as that with the greatest value of the $\max|B_d^G|$ test statistic comparing its distribution of magnitude-breadth curves versus the pooled placebo group.

Superiority comparisons of vaccine regimens passing the tier-2 screen

Similarly, the $\max|B_d^G|$ test statistic will be used to compare the distribution of magnitude-breadth curves between each pair of advanced vaccine regimens. The Holm-Bonferroni procedure will be applied to determine the pairs of regimens with significant differences in distribution controlling the family-wise false positive error rate at no more than 0.05. Nominal (unadjusted) 95% CIs about pairs of vaccine arms will also be reported.

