Overall, the goal of the trial is to elicit tier-2 neutralizing antibodies against FP with breadth. Key immunological questions to be addressed include: 1) Will somatic hypermutation allow focusing on FP during the priming phase?, 2) What is the impact of FP priming on inducing a cross-reactive HIV-1 neutralizing response?, 3) What are the differences in immune responses and types of antibodies elicited by different priming regimens, either priming with FP alone or FP in combination with a stabilized Env trimer?, and 4) Will boosting with diverse trimers and trimer cocktails induce and expand breadth of neutralization responses? This trial continues a project establishing first-in-human data for adjuvanted stabilized Env trimers in combination with the adjuvanted FP vaccine, which has already shown promise in animal models. Data from this trial will be used in design of future antigens and vaccine regimens to increase breadth and potency of FP-directed neutralization as a critical step towards development of a protective HIV-1 vaccine.

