2.5 Rationale for Vaccine Regimen and Dose Selections

The consecutive immunization strategy through the sequential prime-boost regimens allows for the ability to induce potent HIV-1 broadly neutralizing antibodies (bnAb) in animal studies (46). Investigation of different prime-boost regimens may inform on the next generation of HIV-1 vaccines and the immunization regimens capable of eliciting durable, cross-reactive serum neutralizing antibody responses in humans. The pre-clinical studies provide

substantial evidence that an epitope-focused vaccine approach using an FP-carrier protein conjugate (FP8v1-rTTHC) and prefusion-closed stabilized Env trimer(s) (Trimer 4571 and Trimer 6931) administered with an adjuvant (ie, Adjuplex) in a prime-boost regimen can elicit reproducible, neutralizing immune responses against diverse tier-2 primary isolates in animals. In addition, they indicate that a FP-fusion protein + Trimer 4571 prime cocktail, followed by heterologous boosts by each individual trimer and then with a cocktail of the two trimers, has induced the broadest neutralizing response to the FP epitope. These animal studies provide the rationale for Groups 7 and 8 in Part B of this study, which tests the difference in the two priming regimens of FP-conjugate alone (Group 7) or FP-conjugate + Trimer 4571 cocktail (Group 8). Group 6 is an essential control arm, which tests the relative effects of each booster regimen for Groups 7 and 8. The first 4 doses in Group 6 mirror the boosts for Group 7 and the last 3 doses mirror the boost doses in Group 8. This will provide important data on the trimers alone and in cocktail to induce immunity in combination with Adjuplex and importantly, will allow a precise determination the impact of FP and FP + trimer priming. These data can confirm whether the animal study results were predictive, and thus can inform future product development.

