3.2 Exploratory objectives

Exploratory objective 1:

Mapping of FP-specific serum neutralizing activity

Exploratory objective 2:

To evaluate the ability of the vaccine regimen to elicit early FP broad neutralizing antibody memory B-cell lineages.

Exploratory objective 3:

To evaluate the humoral and cellular immune response to vaccination regimens including FP-conjugate vaccine and Trimer 4571 to compare responses between the regimens.

Exploratory objective 4:

To conduct analyses related to furthering the understanding of HIV, immunology, vaccines, and clinical trial conduct. To further evaluate immunogenicity of each vaccine regimen, additional immunogenicity assays may be performed in a subset of participants, including on samples from other timepoints, based on the HVTN Laboratory Assay Algorithm.

4 Laboratory strategy

The laboratory strategy for this protocol will focus on interrogations of the humoral and cellular immune response as it relates to the ability of FP-conjugate and Trimer 4571 vaccines to elicit FP-specific binding antibodies. ~~the elicitation of broadly neutralizing antibodies. Magnitude, breadth, kinetics and durability of serum neutralizing antibodies will be assessed by using vaccine-matched and non-matched (heterologous) tier 2 HIV-1 Env pseudotyped viruses in the TZM-bl assay. Serum antibodies will be further interrogated by measuring IgG binding to the vaccine antigens and a specialized set of epitope-domain-specific antigens. A role for T cell help will be investigated by assessing antigen-specific CD4+ T cells by intracellular cytokine staining as measured by flow cytometry. To gain further insights into the requirements for broadly neutralizing antibody induction, exploratory studies may be conducted to assess antigen-specific B-cell frequencies and to interrogate B-cell lineages that give rise to FP-specific antibodies in vaccine recipients. Serum neutralizing antibodies may also be assessed in the TZM-bl assay. The detailed laboratory strategy and the technical details are described in the Central Assay Plan and will be updated as new reagents and techniques are incorporated into assay planning. This document will be available on the protocol webpage. Descriptions of the standard HVTN laboratory assays can be found online at~~
<https://www.hvtn.org/content/dam/hvtn/scientific-programs/hvtn-laboratory-assay-descriptions.pdf>

5 Study design

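### The formal AUC-MB superiority tests leave out any arm that fails the screen against baseline, so a contrast with the control arm, Group 6, is not guaranteed

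*Protocol*

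**What the plan says.** **The screen.** In Protocol 6.5.4.3, "Dunnett's procedure will be applied with 2-sided alpha = 0.05 to determine which of the 3 vaccine groups (Groups 6-8 in Part B") exceed baseline in mean AUC-MB. The three differences get confidence intervals "versus the pooled baseline samples from Groups 6-8, which simultaneously have at least 95% coverage probability". Group 6 is screened like the other two. Arms that pass are ranked by mean AUC-MB and the highest is selected.

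**The superiority step.** Protocol 6.5.4.4 continues: "For the set of vaccine regimens that passed the tier-2 screen, an F-test will be performed for whether any of the mean AUC-MBs differ". In the interval formula, N and m count only the arms that advanced. For the distribution statistic max|B|, the "test statistic will be used to compare the distribution of magnitude-breadth curves between each pair of advanced vaccine regimens", with Holm-Bonferroni adjustment. Each block ends with a sentence promising nominal 95% intervals, which speaks of pairs of vaccine arms rather than of advanced regimens.

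**The question.** Protocol 2.1 lists as a key question: "What is the impact of FP priming on inducing a cross-reactive HIV-1 neutralizing response". Protocol 2.5 says: "Group 6 is an essential control arm, which tests the relative effects of each booster regimen for Groups 7 and 8". Exploratory objective 3 in Protocol 3.2 is to evaluate immune responses "to compare responses between the regimens", with no mention of a screen.

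**The general rule.** Protocol 6.5.4.1 gives TZM-bl neutralization as its first example of quantitative data. It tests all vaccine arms together and then pairwise if the overall test is significant, with no screen.

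**The concern.** The null tested in 6.5.4.4 is equality among the arms that passed. It is not equality of the FP-containing arms and the control. If Group 6 stays near baseline while Groups 7 and 8 rise, the formal step compares only 7 with 8. If a single arm passes, it compares nothing.

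That outcome is plausible. Protocol 2.1 reports that stabilized trimers gave limited breadth in animals, the AUC-MB panel is heterologous tier 2, and Group 6 received one dose. The reader would then know that one arm beat baseline and another did not, which is not evidence that the two arms differ. At stake is the estimate and test of what FP adds.

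**Working it through.** **1. The plan's own figure.** No power is given for AUC-MB, or for any contrast with Group 6. The nearest figure is Table 6-5: Group 7 vs Group 8, 9 per arm, all responding, Wilcoxon test, 1.5 SD for 80% power. Simulating the exact rank-sum test with normal data gives 0.80 at 1.5 SD, so it reproduces. At the tabled 1.8 SD for 90% power I get 0.92.

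**2. Inputs.**
- Group 6, n = 10: 10 enrolled, and 6.2.1 gives 13 for Groups 5 and 6 together, less 3 in Group 5.
- Groups 7 and 8, n = 9 each (6.2.1).
- Pooled baseline, n = 10 + 10 + 9 = 29.
- Common SD, as the variance term in 6.5.4.4 implies.
- Baseline treated as independent of the post-vaccination samples. This is my simplification, since they come from the same people.
- Effects in SD units above baseline. These are assumptions, so a range is shown.

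**3. What Group 6 needs to pass.** Residual degrees of freedom are 10 + 9 + 9 + 29 − 4 = 53. The simulated two-sided Dunnett critical value is 2.45. Group 6's observed mean must exceed baseline by

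2.449 × √(1/10 + 1/29) = 2.449 × 0.367 ≈ 0.90 SD.

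**4. Chance that Group 6 fails.** Approximately Φ((0.90 − δ)/0.367), where δ is its true effect. For δ = 0.5 this is Φ(1.09) ≈ 0.86, and for δ = 1.0 it is Φ(−0.27) ≈ 0.39. Simulation gives 85% and 39%. The size of the FP effect does not enter the formula.

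**5. Power against Group 6.** I set Groups 7 and 8 a further 1.5 SD above Group 6. *Gated* is the written procedure (screen, then F-test and LSD among passing arms). *Ungated* is the same F-test and LSD on all three arms. With 9 in each of Groups 7 and 8, the results hold equally for 8 vs 6 and 7 vs 6.

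| Group 6 true effect (SD) | Group 6 fails screen | Contrast made | Gated power | Ungated power |
|---|---|---|---|---|
| 0 | 99% | 0.9% | 0.3% | 85% |
| 0.5 | 85% | 15% | 9% | 85% |
| 1.0 | 39% | 61% | 48% | 85% |
| 1.5 | 5% | 95% | 80% | 85% |
| 2.0 | 0.2% | 99.8% | 85% | 85% |

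**6. Sensitivity.** At the originally planned 15 per group (baseline 45), Group 6 fails 99%, 77%, 18% and 0.5% of the time at 0, 0.5, 1.0 and 1.5 SD. The larger trial would have eased the problem for a moderate Group 6 response but not for a weak one.

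**7. After the fix.** A direct two-sided 0.05 t-test at 10 vs 9 has power 54%, 73% and 87% for differences of 1.0, 1.25 and 1.5 SD, before any adjustment for two contrasts.

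**The case against.** Four replies deserve weight.

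- **Other parts of the plan may supply the contrast.** The unscreened test in 6.5.4.1 names TZM-bl data, and nothing in 6.5.4.3 or 6.5.4.4 says it is displaced. The nominal-interval sentences are worded for vaccine arms. The LSD intervals already use the unadjusted t percentile, so after a significant F-test nominal intervals on the same pairs would add nothing, which hints at a wider scope. The optional omnibus comparison is also worded for vaccine arms. Against this, 6.5.4.5 and 6.5.4.6 explicitly send the BAMA and ICS analyses to the general approach and 6.5.4.4 does not, and the nominal-interval sentences sit under headings limited to passing regimens. The point is open. A reader might infer that no comparison with Group 6 would be made at all; the documents do not support that.

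- **Group 6 need not fail.** A reader might infer that the control drops out whenever FP priming works. Steps 4 and 5 show otherwise: exclusion depends on Group 6's own response, and at +1.5 SD or more little power is lost. Protocol section 5 expects the vaccines to induce a detectable response, and nowhere is Group 6 expected to stay at baseline.

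- **Group 7 vs Group 6 no longer isolates FP.** The boosts that made Group 6 a control were never given. Group 7 received only FP conjugate and Group 6 one dose of Trimer 4571. This stands: only 8 vs 6 isolates adding FP.

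- **The stakes are lower in version 2.0.** Neutralization is exploratory, the assays are optional (2.6), and the primary immunogenicity endpoint is MSD binding, which the screen does not touch. This also stands.

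One further number can mislead. If all three arms truly sit at +0.8 to +1.0 SD, exactly one of Groups 6 and 7 passes in about 39–41% of trials. That is not an error rate of the plan, because no section infers a difference from a pass and a fail. It shows only why such an inference should be ruled out.

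**Conclusion.** The concern holds in limited form. A written rule, not a missing detail, can remove Group 6 from both formal AUC-MB comparisons, and no sentence clearly restores it. The SAP supplied covers safety only and does not settle the matter.

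The loss runs from nearly all power when Group 6 is at baseline to about 5 points when it responds by 1.5 SD, and to none at 2 SD. These figures rest on assumed effect sizes, normal data with a common SD, and an independent pooled baseline. They describe the gated procedure alone, not every analysis the protocol permits. The change is worth making because it is cheap, although an exploratory endpoint limits its weight.

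**What to change.** In Protocol 6.5.4.4:

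1. Run the F-test and LSD step, and the max|B| pair comparisons, on Groups 6, 7 and 8 whether or not they pass the screen.
2. Keep the screen for the statement about each arm against baseline and for selecting the best regimen.
3. Always report the difference in mean AUC-MB with a 95% CI at 2 weeks after dose 1, when every arm has had one dose. Give it for 8 vs 6, as the contrast that isolates adding FP to Trimer 4571, and for 7 vs 6, labelled as a comparison of two different priming immunogens.
4. State that the nominal intervals cover all pairs, and whether the 6.5.4.1 tests also apply to AUC-MB.
5. State that one arm passing and another failing is not evidence that they differ.

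The cost is wording, up to two more pairwise contrasts and a slightly larger multiplicity adjustment. No new samples or assays are needed.
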